4.5.15.5 Consent to Participate in the Research Biosample Repository

The Informed Consent Form will contain a separate section that addresses participation in the RBR. The investigator or authorized designee will explain to each patient the objectives, methods, and potential hazards of participation in the RBR. Patients will be told that they are free to refuse to participate and may withdraw their consent at any time and for any reason during the storage period. A separate, specific signature will be required to document a patient's agreement to provide optional RBR samples. Patients who decline to participate will not provide a separate signature. The investigator should document whether or not the patient has given consent to participate and (if applicable) the date of consent, by completing the Sample Informed Consent/Withdrawal eCRF.

In the event of an RBR participant's death or loss of competence, the participant's samples and data will continue to be used as part of the RBR research.

4.5.15.6 Withdrawal from the Research Biosample Repository

Patients who give consent to provide RBR samples have the right to withdraw their consent at any time for any reason. After withdrawal of consent, any remaining samples will be destroyed. However, if RBR samples have been tested prior to withdrawal of consent, results from those tests will remain as part of the overall research data. If a patient wishes to withdraw consent to the testing of his or her RBR samples during the study, the investigator must inform the Medical Monitor in writing of the patient's wishes through use of the appropriate RBR Subject Withdrawal Form and must enter the date of withdrawal on the Sample Informed Consent/Withdrawal eCRF. If a patient wishes to withdraw consent to the testing of his or her RBR samples after closure of the site, the investigator must inform the Sponsor by emailing the study number and patient number to the following email address:

[contact]

A patient's withdrawal from this study does not, by itself, constitute withdrawal of consent for testing of RBR samples. Likewise, a patient's withdrawal of consent for testing of RBR samples does not constitute withdrawal from this study.

4.5.15.7 Monitoring and Oversight

RBR samples will be tracked in a manner consistent with Good Clinical Practice by a quality-controlled, auditable, and appropriately validated laboratory information management system, to ensure compliance with data confidentiality as well as adherence to authorized use of samples as specified in this protocol and in the Informed Consent Form. Sponsor monitors and auditors will have direct access to appropriate parts of records relating to patient participation in the RBR for the purposes of verifying the data provided to the Sponsor. The site will permit monitoring, audits, IRB/EC review, and health authority inspections by providing direct access to source data and documents related to the RBR samples.

4.6 TREATMENT, PATIENT, STUDY, AND SITE DISCONTINUATION

4.6.1 Study Treatment Discontinuation

A patient must permanently discontinue study treatment if any of the following criteria are met:

- Any medical condition that the investigator or Sponsor determines may jeopardize the patient's safety if he or she continues to receive study treatment
- Investigator or Sponsor determination that treatment discontinuation is in the best interest of the patient
- Pregnancy
- Serious adverse event related to study drug in the opinion of the investigator and Sponsor
- Clinically significant Grade ≥ 3 adverse event, as determined by the investigator, related to study drug
- Persistent (>2 hours) Grade 1 bleeding
- [REDACTED]
- [REDACTED]
- [REDACTED]
- INR ≥ 4 and Grade 3 or Grade 4 bleeding
- [REDACTED]
- ALT or AST elevation $\geq 3 \times$ ULN in combination with either total bilirubin $\geq 2 \times$ ULN or clinical jaundice (Hy's Law; see Section [5.3.5.6](#))
- Episode of torsades de pointes (unless there is a clear alternative cause for the changes)

- Sustained (at least two ECG measurements > 30 minutes apart) QTcF that is > 500 ms and > 60 ms longer than the baseline value or sustained QTcF > 515 ms (unless there is a clear alternative cause for the changes)
- Patient requirement for a prohibited therapy (see Section 4.4.2)

The IMC will review any event suggestive of a significant safety risk to patients. Study treatment for all enrolled patients may be paused or discontinued pending IMC review if any of the following criteria are met in two or more patients:

- Elevated ALT or AST in combination with either an elevated bilirubin or clinical jaundice as defined by Hy's law (see Section 5.3.5.6)
- Sustained (at least two ECG measurements > 30 minutes apart) QTcF that is > 500 ms and > 60 ms longer than the baseline value or sustained QTcF > 515 ms (unless there is a clear alternative cause for the changes)
- Episode of torsades de pointes (unless there is a clear alternative cause for the changes)

The primary reason for study treatment discontinuation should be documented on the appropriate eCRF. Patients who discontinue study treatment prematurely will not be replaced.

Patients will return to the clinic for a treatment completion or treatment discontinuation [REDACTED] days after the final dose of study drug.

Refer to the schedule of activities (see [Appendix 1](#)) for details on follow-up assessments to be performed for patients who permanently discontinue study treatment. If a patient requests to be withdrawn from treatment or follow-up assessments, this request must be documented in the source documents and signed by the investigator.

4.6.2 Patient Discontinuation from the Study

Patients will return to the clinic for a study completion or study discontinuation visit at [REDACTED] after the last dose of study drug.

Patients have the right to voluntarily withdraw from the study at any time for any reason. In addition, the investigator has the right to withdraw a patient from the study at any time.

Reasons for patient discontinuation from the study may include, but are not limited to, the following:

- Patient withdrawal of consent
- Study termination or site closure
- Adverse event
- Loss to follow-up

- Patient non-compliance, defined as failure to comply with protocol requirements as determined by the investigator or Sponsor

Every effort should be made to obtain a reason for patient discontinuation from the study. The primary reason for discontinuation from the study should be documented on the appropriate eCRF. If a patient requests to be withdrawn from the study, this request must be documented in the source documents and signed by the investigator. Patients who withdraw from the study will not be replaced.

4.6.3 Study Discontinuation

The Sponsor has the right to terminate this study at any time. Reasons for terminating the study may include, but are not limited to, the following:

- The incidence or severity of adverse events in this or other studies indicates a potential health hazard to patients
- Any event or scenario leading to permanent cessation of dosing in all patients (Section 4.6.1) and for which the IMC (in consultation with the investigator) cannot identify an adequate risk mitigation measure or therapeutic margin
- Patient enrollment is unsatisfactory

The Sponsor will notify the investigator if the Sponsor decides to discontinue the study.

4.6.4 Site Discontinuation

The Sponsor has the right to close a site at any time. Reasons for closing a site may include, but are not limited to, the following:

- Excessively slow recruitment
- Poor protocol adherence
- Inaccurate or incomplete data recording
- Non-compliance with the International Council for Harmonisation (ICH) guideline for Good Clinical Practice
- No study activity (i.e., all patients have completed the study and all obligations have been fulfilled)

5. ASSESSMENT OF SAFETY

5.1 SAFETY PLAN

GDC-6599 is not approved, and clinical development is ongoing. The safety plan for patients in this study is based on nonclinical data and clinical experience with GDC-6599 in the *completed* first-in-human Phase Ia/b SAD and MAD study in healthy volunteers (Study GA43010).

However, the full spectrum of risks in humans has not yet been fully characterized. Therefore, the anticipated potential/theoretical risks for GDC-6599 outlined below are based on the anticipated mechanism of action and results from nonclinical studies.

GDC-6599—Genentech, Inc.

67/Protocol GA43590, Version 4

Please refer to GDC-6599 Investigator's Brochure for a complete summary of safety information.

The mannitol challenge test is a commercially approved bronchial challenge test kit containing prefilled mannitol capsules and a handheld dry powder inhaler device. Please refer to local prescribing information for a complete summary of safety information.

Several measures will be taken to ensure the safety of patients participating in this study. Eligibility criteria have been designed to exclude patients at higher risk for toxicities (see Section 4.1). Patients will undergo safety monitoring during the study, including assessment of the nature, frequency, and severity of adverse events. In addition, guidelines for managing adverse events, including criteria for treatment interruption or discontinuation, are provided below.

5.1.1 Risks Associated with GDC-6599

5.1.1.2 Impaired Cough Reflex

Ion channels of the TRP class are important in the afferent sensory loop of the cough reflex and in the heightened cough sensitivity seen in disease. There is growing evidence for both TRPV1 and TRPA1 in peripheral sensitization and cough (Morice et al. 2014). Specifically, TRPA1 is expressed in small diameter, nociceptive neurons in the airways, where its activation by cold temperatures and environmental irritants may contribute to the perception of noxious stimuli and the stimulation of vagal sensory afferent neurons leading to central reflexes including cough, which is necessary to remove the foreign material from the respiratory tract (Grace et al. 2011). For this reason, there is a theoretical risk that inhibition of TRPA1 may impair normal cough reflexes.

As a result, antagonists of TRPA1, such as GDC-6599, may reduce sensitivity to foreign material in the airways, which may increase the risk of aspiration pneumonitis and lower respiratory tract infections. Individuals with a history of recurrent lower respiratory tract infections, such as pneumonia, have been shown to have a decreased response to capsaicin, an agonist of TRPV1 (Niimi et al. 2003). It is unknown whether this association is unique to TRPV1 or generalizable to other TRP-class ion channels. Conversely, in patients with a history of severe asthma, increased sensitivity to capsaicin was associated with poorer asthma control, suggesting that in pathogenic processes such as asthma, the cough reflex is maladaptive (Kanemitsu et al. 2020).

Animal studies of GDC-6599 found no evidence of impairment in cough or increased risk of lower respiratory tract infections. However, animals included in toxicity studies are healthy, are prescreened for certain infectious agents with negative test results before study start, and are housed in a controlled laboratory environment that limits the risks of infections. Thus, the absence of findings may not be predictive of the risk for human subjects.

Patients with a history of aspiration will be excluded from participating in the study (see Section 4.1.2), and patients will be closely monitored for respiratory tract infections.

Guidelines for management of patients who develop lower respiratory tract infections are provided in Section 5.1.3.2.

[REDACTED]

[REDACTED]

5.1.2 Potential Risks Associated with Mannitol Challenge Test

Investigators should be aware of the risks associated with the mannitol challenge test and guidelines for managing those risks. Please refer to the local prescribing guidelines for the mannitol challenge test (Aridol®/Osmohale®) for full information.

5.1.2.1 Severe Bronchospasm

Mannitol acts as a bronchoconstrictor and may cause severe bronchospasms in susceptible patients. The test should only be conducted by trained professionals under the supervision of a physician familiar with all aspects of the bronchial challenge test and the management of acute bronchospasm. Patients should not be left unattended during the bronchial challenge test. Medications and equipment to treat severe bronchospasm must be present in the testing area. If severe bronchospasm occurs, it should be treated immediately by administration of a SABA. Because of the potential for severe bronchoconstriction, the bronchial challenge testing with mannitol should not be performed in any patient with very low baseline pulmonary function tests (e.g., $FEV_1 < 1-1.5$ liters or $< 60\%$ of the predicted values)

If a patient has a $\geq 10\%$ reduction in FEV_1 (from pre-challenge FEV_1) on administration of the 0 mg capsule, the mannitol challenge test should be discontinued and the patient should be given a dose of an inhaled SABA and monitored accordingly.

Patients with either a positive response to bronchial challenge testing with mannitol or significant respiratory symptoms should receive an inhaled SABA. Patients should be monitored until fully recovered to within baseline FEV₁.

5.1.2.2 Potential Effects in Patients with Comorbid Conditions

Bronchial challenge testing with mannitol should be performed with caution in patients with conditions that may increase sensitivity to the bronchoconstriction or other potential effects of mannitol, such as severe cough, ventilatory impairment, spirometry-induced bronchoconstriction, hemoptysis of unknown origin, pneumothorax, recent abdominal or thoracic surgery, recent intraocular surgery, unstable angina, or active upper or lower respiratory tract infection.

5.1.3 Management of Patients Who Experience Specific Adverse Events

5.1.3.1 Dose Modifications and Treatment Interruption

Dose modification and treatment interruption is not allowed in this study. Guidelines for management of specific adverse events are outlined in [Table 4](#) below.

5.1.3.2 Management Guidelines

Guidelines for management of specific adverse events are outlined in [Table 4](#).

Additional guidelines are provided in the subsections below. These guidelines are intended to inform rather than supersede an investigator's clinical judgment and assessment of the benefit–risk balance when managing individual cases.

Table 4 Guidelines for Management of Patients Who Experience Adverse Events

Event	Action to Be Taken
Coagulation abnormalities	
Grade ≥ 3 PT prolongation (PT $\geq 1.5 \times$ ULN)	
Discontinue study drug.
INR of > 2 and < 4	
Administer Vitamin K (2.5 mg PO $\times 1$).Repeat coagulation parameters daily until INR improves to < 1.5.

Table 4 Guidelines for Management of Patients Who Experience Adverse Events (cont.)

Event	Action to Be Taken
Coagulation abnormalities	
INR ≥ 4 without evidence of bleeding	
 • Contact Medical Monitor. • Administer Vitamin K (10 mg PO daily) until INR < 1.5 and at least 5 GDC-6599 drug-elimination half-lives have elapsed (estimated to be 4 days). • If no response to Vitamin K, consider administering PCC or FFP. • Consider subspecialist (hematology) consultation.
INR ≥ 4 and Grade 3 or Grade 4 bleeding	
 • Discontinue study drug. • Administer 4-factor PCC or FFP.
Impaired cough reflex	

FFP=fresh frozen plasma; GGT= gamma-glutamyl transferase; IDSA=Infectious Diseases Society of America; PCC=prothrombin complex concentrate; ULN=upper limit normal; PO=by mouth.

^a https://www.idsociety.org/practice-guideline/practice-guidelines/#/date_na_dt/DESC/0/+/.

5.1.3.3 Management of Increases in QT Interval

Study drug should be discontinued in patients who develop any of the following, unless there is a clear alternative cause for the changes:

- Sustained (at least two ECG measurements >30 minutes apart) QTcF that is >500 ms and >60 ms longer than the baseline value
- Sustained absolute QTcF that is >515 ms
- An episode of torsades de pointes or a new ECG finding of clinical concern

Of note, if there is a new intraventricular conduction block, the increase in QRS complex duration should be subtracted from the QTcF change, because this represents an increase in QTcF unrelated to alterations in repolarization. Also of note, it is not uncommon to record arrhythmias such as non-sustained ventricular tachycardia, supraventricular tachycardia, pauses, or atrial fibrillation in healthy volunteers receiving placebo during periods of extended ECG monitoring. Therefore, it is critical that expert cardiology advice be sought to confirm any ECG changes and to ascertain the likelihood of a drug-induced arrhythmia versus the background occurrence of this arrhythmia. In such a situation, saving all available ECG data is highly suggested.

Management of patients with sustained QTcF prolongation should include close monitoring, with ECGs repeated at least hourly until two successive ECGs show resolution of the findings, correction of any electrolyte abnormalities, and possible discontinuation of other concomitant medications that are known to prolong the QT interval. Consultation with a cardiologist or electrophysiologist is recommended, to help in the management of such patients.

In rare circumstances, it may be acceptable to resume study drug, at a lower dose, provided that any ECG abnormalities have resolved and the patient is appropriately monitored. Clinical judgment should be applied.

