4.3.2 Study Treatment Dosage, Administration, and Compliance

The treatment regimens are summarized in Section [3.1](#).

GDC-6599 or placebo will be administered orally at a dose of [REDACTED]. GDC-6599 or placebo tablets should be taken approximately [REDACTED] [REDACTED]. For Visit 2 (Day 1), Visit 4 (Day 14), Visit 5 (Day 30), and Visit 7 (Day 43), [REDACTED] [REDACTED]. Patients may self-administer [REDACTED] [REDACTED] for Visit 3 (Day 7) and Visit 6 (Day 36). Patients will self-administer all other doses of study drug at home.

All active and placebo tablets will be administered by mouth, followed immediately with water. The tablets should be swallowed whole; they should not be chewed, cut, broken, or crushed. Study drug may be taken with or without food. If a dose of study drug is missed (i.e. delayed by more than 4 hours) or if vomiting occurs when the dose is taken, the patient should resume dosing with the next scheduled dose without compensating for the missed dose.

For doses administered in the clinic, compliance will be assessed by a visual check of the mouth and hand performed by site staff. For self-administered doses, patients will be required to record the time they took each dose every day in a study drug compliance electronic diary; missed doses will also be recorded. Patients will be instructed to bring all unused study medication and their study drug compliance diaries to the clinic at specified study visits (see schedule of activities in [Appendix 1](#)). Compliance will be assessed by reviewing diaries and counting returned tablets.

Refer to the pharmacy manual for detailed instructions on drug preparation and administration.

Details on treatment administration (e.g., dose and timing) should be noted on the Study Drug Administration electronic Case Report Form (eCRF). Cases of overdose, medication error, drug abuse, or drug misuse, along with any associated adverse events, should be reported as described in Section 5.3.5.11.

Guidelines for treatment interruption or discontinuation for patients who experience adverse events are provided in Section 5.1.3.1.

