4.5.11 Electrocardiograms

A single 12-lead ECG will be performed at screening to confirm eligibility. If the initial QTcF >450 ms, the ECG should be repeated at least 30 minutes after the first ECG. The patient may be enrolled if second QTcF ≤450 ms. Thereafter, a single 12-lead ECG recording must be obtained for each specified timepoint. Single 12-lead ECG recordings may also be obtained at unscheduled timepoints. Triplicate ECGs are not required; however, ECGs with artifacts that may interfere with interpretation should be repeated.

All ECG recordings must be performed using a standard high-quality, high-fidelity digital electrocardiograph machine equipped with computer-based interval measurements. Lead placement should be as consistent as possible. ECG recordings must be performed after the patient has been resting in a supine position for at least 10 minutes. All ECGs are to be obtained prior to other procedures scheduled at that same time (e.g., vital sign measurements, blood draws) and should not be obtained within 3 hours after any meal. Circumstances that may induce changes in heart rate, including environmental distractions (e.g., television, radio, conversation) should be avoided during the pre-ECG resting period and during ECG recording.

For safety monitoring purposes, the investigator must review, sign, and date all ECG tracings. Paper copies of ECG tracings will be kept as part of the patient's permanent study file at the site. Digital recordings will be stored at the site. The following should be recorded in the appropriate eCRF: heart rate, RR interval, QRS interval, PR duration, uncorrected QT interval, and QTcF based on the machine readings of the individual ECG tracings. Any morphologic waveform changes or other ECG abnormalities must be documented on the eCRF. If considered appropriate by the Sponsor, ECGs may be analyzed retrospectively at a central laboratory.

If at a particular timepoint the mean QTcF is >500 ms and/or >60 ms longer than the baseline value, another ECG must be recorded, ideally within the next 5 minutes, and

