ECG monitoring should continue until QTcF has stabilized on two successive ECGs. The Medical Monitor should be notified. Standard-of-care treatment may be instituted per the discretion of the investigator. If a PK sample is not scheduled for that timepoint, an unscheduled PK sample should be obtained. A decision on study drug discontinuation should be made, as described in Section 5.1.3.3. The investigator should also evaluate the patient for potential concurrent risk factors (e.g., electrolyte abnormalities, co-medications known to prolong the QT interval, severe bradycardia).

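### Section 5.1.3.3 allows a lower-dose restart after a QT/ECG event, which Section 5.1.3.1 bars outright and Section 4.6.1 bars for the listed QTcF and torsades events without a clear alternative cause

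*Combined protocol and SAP*

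**What the plan says.** Three sections of the combined protocol and SAP set the rule for a patient with a QT event.

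- **Section 5.1.3.3** says study drug should be stopped for any of four findings unless there is a clear alternative cause. Two are sustained QTcF thresholds: >500 ms together with >60 ms over baseline, and >515 ms. The other two share one bullet: "An episode of torsades de pointes or a new ECG finding of clinical concern". The section closes with the permission: "In rare circumstances, it may be acceptable to resume study drug, at a lower dose, provided that any ECG abnormalities have resolved". The patient must also be appropriately monitored, and clinical judgment applies.
- **Section 5.1.3.1** says: "Dose modification and treatment interruption is not allowed in this study". It gives no QT exception.
- **Section 4.6.1** opens its list with "A patient must permanently discontinue study treatment if any of the following criteria are met". The list includes both QTcF thresholds and "Episode of torsades de pointes (unless there is a clear alternative cause for the changes"). The QTcF item carries the same carve-out.

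Two cross-references decide which of these an investigator reads. The ECG section (4.5.11) says: "A decision on study drug discontinuation should be made, as described in Section 5.1.3.3". The dosing section (4.3.2) says: "Guidelines for treatment interruption or discontinuation for patients who experience adverse events are provided in Section 5.1.3.1". Neither mentions Section 4.6.1.

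**The concern.** For the same patient with the same ECG, one section requires a permanent stop, one forbids any interruption or dose change, and one permits a restart at a reduced dose. An investigator dealing with an acute QT event who follows the ECG section arrives at the permissive text and is not directed to the mandatory rule.

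What is at stake is patient safety more than estimation: possible re-exposure to GDC-6599 after a qualifying QTcF prolongation or torsades. Section 4.6.1 treats these same events, when seen in two or more patients, as grounds for pausing or stopping treatment in everyone pending committee review. There is also a compliance problem. A site that used the permission would breach Section 5.1.3.1, and Section 9.2 allows no prospective request to deviate.

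**Working it through.** The plan gives no figure to reproduce. The check compares the sections and then asks when a restart could arise.

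**Step 1: triggers against rules.** Stopping and then resuming at a lower dose is both an interruption and a dose modification, so Section 5.1.3.1 is engaged whatever the trigger or cause. A permanent stop is neither.

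| Trigger in 5.1.3.3 | Listed in 4.6.1? | Restart against 5.1.3.1 | Restart against 4.6.1, no clear alternative cause |
|---|---|---|---|
| Sustained QTcF >500 ms and >60 ms over baseline | Yes | Conflict | Conflict |
| Sustained QTcF >515 ms | Yes | Conflict | Conflict |
| Torsades de pointes | Yes | Conflict | Conflict |
| Other new ECG finding | No | Conflict | No QT-specific rule |

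Count: 4 of 4 against Section 5.1.3.1, and 3 of 4 against Section 4.6.1.

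**Step 2: is there reconciling text?** Three places come close.

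- Section 5.1.3.2 describes the management guidelines as informing clinical judgment. It does not waive a mandatory stop in another section.
- Section 3.1.2 lets the Internal Monitoring Committee recommend a change of dose level or frequency. That follows committee safety review, with the final decision left to the Sponsor's study team. It is not an investigator restarting one patient.
- Sections 5.3.5.4 and 5.3.5.5 mention dosage modification only as an example of what makes an abnormal result reportable.

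**Step 3: when could re-exposure within a period arise?** Section 4.3.2 puts Visits 2, 4, 5 and 7 on Days 1, 14, 30 and 43. Appendix 1 schedules the treatment-period ECGs at those visits and says assessments on in-clinic dosing days precede the dose unless otherwise specified. Dosing runs over Days 1–14 and 30–43, which is 14 days per period.

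| Scheduled ECG (nominal day) | Earlier dosing days in period | Later dosing days in period |
|---|---|---|
| Day 1 | 0 | 13 |
| Day 14 | 13 | 0 |
| Day 30 | 0 | 13 |
| Day 43 | 13 | 0 |

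No scheduled day (0 of 4) has both counts above zero. On Days 14 and 43 only same-day dosing remains. Same-period re-exposure therefore depends mainly on extra recordings, which Section 4.5.11 allows: "Single 12-lead ECG recordings may also be obtained at unscheduled timepoints". A post-dose unscheduled ECG on dosing day d leaves at most 14 − d later dosing days. For d = 1 that is 14 − 1 = 13, and for d = 13 it is 14 − 13 = 1. Time for the ECG to resolve must be subtracted, and the drug is active only in the GDC-6599 period. Calendar days are used because the daily regimen is redacted.

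**The case against.** The best defence is that the texts can be ranked. Section 5.1.3.2 calls its content guidelines, Section 5.1.3.3 speaks of what should be done or may be acceptable, and Section 4.6.1 says what must be done. A careful reader could let the mandatory rule prevail. That is reasonable, but the protocol does not say so, and its ECG section points to the permissive text. Arguing that a specific QT rule overrides a general dosing rule might answer Section 5.1.3.1. It cannot answer Section 4.6.1, which is just as specific.

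The second defence is that the risk is well contained, and this largely stands:

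- Section 4.1.2 excludes QTcF >450 ms, subject to one repeat ECG, and Section 4.4.2 prohibits QT-prolonging drugs through Visit 8.
- Section 5.1.3.3 makes the restart conditional on ECG resolution and monitoring. It calls expert cardiology advice critical for confirming ECG changes.
- Section 4.5.11 requires the Medical Monitor to be told, and Section 4.6.1 has the committee review any event suggesting a significant safety risk.
- A drug-related event may also meet another mandatory stop in Section 4.6.1, such as a related serious adverse event.
- The restart is optional, so a site that stops permanently breaches nothing.

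These points limit the size of the problem without saying which rule governs.

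A reader might also infer that where a clear alternative cause exists the restart breaks Section 4.6.1. It does not, because that section carries the same exception. In such a case Section 5.1.3.3 does not call for stopping either, so there is something to resume only if drug was held first. Section 5.1.3.1 would still bar that restart.

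**Conclusion.** The contradiction stands and should be corrected. Any restart under Section 5.1.3.3 conflicts with Section 5.1.3.1. For the two sustained QTcF thresholds and torsades, it also conflicts with Section 4.6.1 unless there is a clear alternative cause. The practical risk is small.

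Four stronger readings are tempting, and the documents do not support them.

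- A reader might infer that the sections also disagree on whether Period 2 may start after a Period 1 event. Section 5.1.3.3 never mentions Period 2. It speaks of resuming at a lower dose, not of starting the alternate treatment.
- A reader might infer that omitting the fourth trigger from Section 4.6.1 is itself an error. That finding is undefined, and Section 5.1.3.3 warns that some arrhythmias are not uncommon on placebo during extended monitoring. Whether it should force a permanent stop is a clinical trade-off, since discontinued patients are not replaced.
- A reader might take the 0-of-4 count as fixed. It holds for the nominal days in Section 4.3.2. The visit-window footnotes to Appendix 1 are not visible, and an early Visit 4 or 7 would change it.
- A reader might infer that a lower dose could not be supplied. Tablets may not be cut or broken and the visible text describes no lower-dose supply, but the strength is redacted, so feasibility is unknown.

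**What to change.** 1. Delete the resumption sentence from Section 5.1.3.3.
2. Add there that study drug stopped under that section is not restarted, citing Sections 5.1.3.1 and 4.6.1. Do not word this as permanent unless there is an alternative cause, because that could be read as allowing an interruption, which Section 5.1.3.1 bars.
3. Have Section 4.5.11 cite Section 4.6.1 as well as Section 5.1.3.3.

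Leave the mandatory list in Section 4.6.1 as it is.

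The cost is one deleted sentence, one added sentence and one cross-reference at the next amendment, plus a memo to sites. Sample size, visit schedule and endpoint definitions do not change. The downside is that a rare patient whose ECG resolves loses a lower-dose restart, which Section 5.1.3.1 already forbids.
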